1.0 Abstract

Glioblastoma (GBM) accounts for 25% of all primary central nervous system (CNS) tumors in adults and historically has been associated with median survival times of less than a year [1]. However, the addition of temozolomide to radiotherapy has resulted in significant improvements in survival, especially for certain subsets of patients [2]. With the improvement in survival times there are growing concerns about the negative effects of treatment, especially the potential for cognitive deficits after cranial radiotherapy. Decreasing the amount of brain exposed to radiation has a significant impact on cognitive function after radiation [3-5]. Proton radiotherapy is a treatment modality which has been safely and effectively used in the treatment of GBMs with low rates of toxicity such as radiation necrosis [6, 7]. Additionally, there is some pre-clinical evidence that supports greater impact on tumor cell death with protons compared to photons [8]. Previous studies have shown that intensity modulated proton therapy (IMPT) can allow for more conformal target coverage than conventional intensity modulated photon radiation therapy (IMRT) while minimizing doses to normal tissues such as the contralateral hippocampus [9]. The decreased dose to critical normal brain tissue resulting from conformal proton radiotherapy has been suggested to translate into improved cognitive function based on radiation dose cognitive effect models [10]. Additionally, improved conformality of dose delivery by IMPT may allow for dose escalation in the treatment of GBM which has been demonstrated to improve median survival time as a result of improved central control of tumors [11]. The purpose of the current study is to prospectively assess the cognitive sequelae, quality of life, and local control outcomes of patient with glioblastoma treated with IMPT versus IMRT.

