Currently most patients with glioblastoma are treated using either 3D conformal or intensity modulated radiation therapy (IMRT) with photon beams. These modalities allow for conformal dosing to tumor while minimizing dose to surrounding normal structures. However,

surrounding normal structures continue to receive low to moderate doses of radiation. Proton beam therapy is an alternative technology which may provide more conformal dosing with less dosing to normal structures.

Proton radiotherapy has been previously demonstrated to be safe and effective in the treatment of high grade gliomas [6, 7, 20]. Additionally, there is preclinical evidence that proton radiotherapy may have a greater impact on tumor cell death. Moertel et al. have demonstrated that human glioblastoma cells in culture experience increased G2 cell cycle arrest and decreased DNA double strand break repair when irradiated with protons versus photons [8]. This suggests a potential advantage of proton therapy in glioblastoma patients.

Previous studies have also demonstrated that IMPT can allow for more conformal dosing than IMRT. IMPT can take advantage of proton characteristics such as less lateral scatter, lack of exit dose, and steep distal dose fall-off to increase conformality. For example, Rosenschold et al. compared treatment plans using IMRT versus IMPT for high grade glioma patients. They found increased planning target volume (PTV) coverage conformality with IMPT. Additionally, IMPT plans had increased sparing of healthy tissue both for whole brain doses as well as to critical structures such as the contralateral hippocampus [9].

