10.0 Criteria for Response and Toxicity

10.1 Definition of primary endpoint:

- 10.1.1 Time to cognitive failure on any of the 6 primary variables from the pre-specified cognitive tests (HVLT-R total recall, HVLT-R delayed recall, HVLT-R delayed recognition, TMT Part A or Part B, COWA) with failure defined as a decline that meets or exceeds the reliable change index (RCI) for each cognitive test variable. A cumulative incidence approach will be used to estimate median time to cognitive failure in order to account for the competing risks of disease progression and death. Patients experiencing disease progression or patients that died prior to experiencing cognitive failure will be considered as having had a competing event. Progressive disease frequently causes cognitive decline, and the goal of this study is to assess the impact of the radiation treatment itself on cognitive decline.
- 10.2 Definitions of secondary endpoints:
 - 10.2.1 Local control and distant control in the brain will be measured by contrast-enhanced brain MRI scan using Response Assessment in Neuro-Oncology (RANO)Criteria, as follows [50].
 - 10.2.1.1 Complete Response (CR): Requires all of the following 1) complete disappearance of all enhancing measurable and non-measurable disease sustained for a minimum of 4 weeks; 2) no new lesions; 3) stable or improving nonenhancing (T2/FLAIR) lesions; 4) patients must be off corticosteroids (or on physiologic replacement doses only); and 5) stable or improved clinically.
 - 10.2.1.2 Partial Response (PR): Requires all of the following: 1) ≥50% decrease compared with baseline in the sum of products of perpendicular diameters of all measurable enhancing lesions sustained for at least 4 weeks; 2) no progression of non-measurable disease; 3) no new lesions; 4) stable or improved non-enhancing (T2/FLAIR) lesions on the same

or lower dose of corticosteroids compared with the baseline scan; 5) stable or improved clinically.

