12.0 Statistical Considerations

- 12.1 Randomization procedure: A stratified block randomization procedure will be used. Randomization will be performed using CORe. The randomization strata are as defined above in section 7.0, and the block size will be 6. Patients who withdraw from the study after randomization, but prior to receiving treatment will be considered a cancel and replaced.
- 12.2 Sample size: With IMRT the cognitive function failure rate at 4 months is 45%, based off of comparative analyses of the cognitive failure rate of RTOG 0614 and compared to the cognitive impairment seen on RTOG 0525; we hope to demonstrate that IMPT can achieve a cognitive function failure rate at 4 months of only 30%. We assume the time to cognitive failure in each treatment arm follows an exponential distribution. A cognitive failure rate of 45% at 4 months then implies a median time to cognitive failure of 4.6 months, while a cognitive failure rate of 30% at 4 months implies a median time to cognitive failure to cognitive failure of 7.8 months.

We will use a 1-sided significance level of 0.20 as suggested by Rubinstein et al. [51]for phase II screening trials. We expect to enroll 2 patients per month, and we will randomize 60 evaluable patients (30 to each treatment arm). We will have 80% power to detect an improvement in cognitive failure at 4 months from 45% in the IMRT arm to 30% in the IMPT arm. We expect to observe 43 events, and the analysis will be performed once we have observed these events. We define evaluable patients as those who have received the assigned treatment *and* completed baseline and at least one follow-up neurocognitive testing. We expect we will need an over accrual of 33% to account for those patients not evaluable. Therefore the target total enrollment sample size is 90 patients to accrue a total of 60 evaluable patients. We expect to observe 43 events, and we expect the trial to take 41 months to observe these events.

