- 12.3 Primary Analysis: The analysis will be performed on the intention-to-treat principle. Considering those patients who are not evaluable as treatment failures. We will use the methods of Gooley et al. [52]to estimate the cumulative incidence of cognitive failure in each treatment arm, considering progressive disease and death before cognitive failure as competing events. We will estimate the cumulative incidence of cognitive failure at 4 months with 95% confidence intervals. We will use the methods of Fine and Gray [53]to test for a difference between treatment arms with respect to the cumulative incidence of cognitive failure, considering progressive disease and death before and death before and death before cognitive failure as competing events. We will use the methods of Fine and Gray [53]to test for a difference between treatment arms with respect to the cumulative incidence of cognitive failure, considering progressive disease and death before cognitive failure as competing events. Our model will include treatment arm and the stratification factors used at randomization.
- 12.4 Secondary Analysis:

We will repeat the primary analysis on only those patients considered evaluable. All the secondary analyses described below will be performed using all patients as well as using only evaluable patients. We will estimate the cumulative incidence of local failure using the methods of Gooley et al. considering death as a competing event. We will model the time to local failure using the methods of Fine and Gray to test for differences between treatment arms, considering death as a competing event. Our model will include treatment arm and the stratification factors used at randomization, as well as selected dosimetric parameters. We will similarly analyze time to distant failure.

We will use the product limit estimator of Kaplan and Meier [54] to estimate overall survival stratified by treatment arm. We will also use Cox proportional hazards regression [55] to model overall survival as a function of treatment arm and the stratification factors used at randomization.

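### The only primary test (Fine-Gray) responds to tumour control as well as cognition, so it can mask a true IMPT benefit; a cause-specific analysis should stand beside it

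*Combined protocol and SAP*

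**What the plan says.** Section 10.1.1 defines the endpoint as time to first cognitive failure, estimated by cumulative incidence: "Patients experiencing disease progression or patients that died prior to experiencing cognitive failure will be considered as having had a competing event". It explains that progression often causes decline and that "the goal of this study is to assess the impact of the radiation treatment itself on cognitive decline".

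Section 12.3 names one test. Fine-Gray is used to "test for a difference between treatment arms with respect to the cumulative incidence of cognitive failure". The rule for patients who progress or die first is "considering progressive disease and death before cognitive failure as competing events". On covariates it says: "Our model will include treatment arm and the stratification factors used at randomization". The 4-month cumulative incidence is estimated with a 95% confidence interval but not tested. The analysis is by intention to treat, with non-evaluable patients counted as failures.

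Section 12.4 repeats this in evaluable patients. It adds Fine-Gray models for local and distant failure, Kaplan-Meier and Cox for survival, mixed models for the cognitive scores, and as-treated versions. It plans no cause-specific hazard model for cognitive failure, and no incidence by arm of progression or death before cognitive failure.

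Two places give a reason why tumour control might differ. Section 1.0 says "there is some pre-clinical evidence that supports greater impact on tumor cell death with protons compared to photons", and Section 4.0 says "there is preclinical evidence that proton radiotherapy may have a greater impact on tumor cell death".

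**The concern.** Cumulative incidence of cognitive failure is built from two rates: cognitive failure among patients still free of progression, and progression or death. An arm that keeps patients progression-free for longer leaves more of them at risk, and so accumulates more cognitive failures even if the monthly risk is unchanged. The question in 10.1.1 is closer to the first rate alone.

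If protons control tumour better, Fine-Gray counts the extra time at risk against IMPT and may miss a real cognitive benefit. If control were worse with IMPT, the bias would run the other way. Without the cause-specific result, neither a positive nor a negative trial could be attributed with confidence to cognition.

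**Working it through.** **1. The plan's own figure.** From 12.2: 4-month failure of 45% and 30%, exponential times, 80% power; "We will use a 1-sided significance level of 0.20".
- Hazards: -ln(0.55)/4 = 0.1495 and -ln(0.70)/4 = 0.0892 per month. Ratio 0.597; medians 4.6 and 7.8 months, as stated.
- Schoenfeld events: 4(0.8416 + 0.8416)²/(ln 0.597)² = 42.5, so 43, as stated.

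No competing hazard enters this calculation.

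**2. Assumed competing hazard.** The documents give no progression rate. Section 4.0 cites 27.2% two-year survival on combined treatment. Under an exponential this is -ln(0.272)/24 = 0.054 per month, a median of 12.8 months. Progression comes no later than death, so 12.8 is taken as the long end and 7 months as the short end.

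**3. How cumulative incidence moves.** With cognitive hazard λ and competing hazard μ, F(t) = λ/(λ+μ) × (1 - exp(-(λ+μ)t)). At a 7-month competing median, μ = ln 2/7 = 0.0990. At 24 months:
- IMRT: 0.1495/0.2485 × (1 - exp(-5.96)) = 0.600.
- IMPT, planned effect, equal control: 0.0892/0.1882 × (1 - exp(-4.52)) = 0.469; difference 0.131.
- IMPT, planned effect, competing hazard 30% lower (0.0693): 0.0892/0.1585 × (1 - exp(-3.80)) = 0.550; difference 0.050.
- IMPT, no cognitive effect, competing hazard 1.5 times higher (0.1485): 0.1495/0.2980 × (1 - exp(-7.15)) = 0.501; difference 0.099.

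In the second and third lines the cause-specific hazard ratio is the same 0.597. In the fourth it is 1.

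**4. Rejection rates, evaluable-only analysis.** Simulation with 30 per arm, 24 months of follow-up, one-sided 0.20, competing median 7 to 12.8 months, cognitive and progression times independent. The comparator is a cause-specific log-rank test.

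| Cognitive effect | Competing hazard, IMPT/IMRT | Fine-Gray | Cause-specific |
|---|---|---|---|
| planned (0.597) | 0.7 | 43-51% | 75-79% |
| planned (0.597) | 1 | 62-65% | 73-78% |
| none | 1 | about 20% | about 20% |
| none | 1.5 | 39-44% | 19-21% |

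With 2,500 runs the standard error is about one point (√(0.4 × 0.6/2500) = 0.0098); repeat runs differ from these ends by about two points. Even the cause-specific test falls short of 80%, because competing events remove cognitive failures: with equal control, 30 × 0.600 + 30 × 0.469 = 32.1 events are expected at a 7-month median and 39.9 at 12.8 months, against the planned 43.

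**5. Intention-to-treat analysis.** Take 45 per arm. Suppose progression or death before a first test at 1 or 2 months counts as failure, with 0 to 33% otherwise non-evaluable.
- No effect, competing hazard 1.5 times higher: Fine-Gray false benefit is about 20-33%.
- Planned effect, competing hazard 0.67 times as high: power is 45-73% with Fine-Gray and 65-90% cause-specific.
- The cause-specific test is disturbed too. Its null rejection ranges over about 12-28% as the ratio of competing hazards goes from 1.5 to 0.67, so part of its power advantage here is an inflated level.

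The result depends on how non-evaluability arises. Adding exactly 15 early failures per arm gives about 29% false benefit at 1.5-fold. If a random 20-33% are non-evaluable for reasons unrelated to tumour control, it is 34-41%, so there is little dampening.

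**The case against.** The strongest defence is that cumulative incidence is a deliberate and legitimate choice. Section 10.1.1 adopts it, 12.2 states the effect as 4-month failure proportions, and Fine-Gray is a valid test of it. That stands: with equal tumour control its level is correct. The 4-month cumulative incidence also moves less (0.379 against 0.349 with no effect, a 1.5-fold competing hazard and a 7-month median), though it is not what is tested.

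Second, a reader might infer that the plan is likely to produce a spurious cognitive benefit. The documents do not support this. It needs worse tumour control with IMPT, whereas Sections 1.0 and 4.0 point to greater tumour cell kill with protons and 7.5 uses the same targets and expansions in both arms. The rule counting non-evaluable patients as failures can also reduce the effect in the primary analysis.

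Third, the local failure, distant failure and survival analyses would help to reveal an imbalance in tumour control. They would, but they do not show progression or death before cognitive failure, nor separate the two mechanisms.

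Fourth, a cause-specific hazard does not cleanly isolate the radiation effect if progression and decline are correlated within patients, as 10.1.1 implies they may be. The stability of the cause-specific column rests on assumed independence. This stands as a limit on the remedy.

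**Conclusion.** The concern holds as a mismatch between the stated goal and the only primary test, and as a missing companion analysis. It does not show that Fine-Gray is invalid or must be replaced.

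Its size depends on tumour control differing by arm. In the direction the background suggests, a 30% lower competing hazard costs Fine-Gray roughly 28 to 32 points of power relative to a cause-specific test (51 against 79, 43 against 75). With equal control, power is lower than with the cause-specific test but the level is sound. The false-benefit scenario is hypothetical.

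These sizes rest on an assumed competing median of 7 to 12.8 months, exponential independent times and the 60 evaluable patients. They should not be read as properties of the intention-to-treat analysis, where the distortion depends on why patients are non-evaluable and the cause-specific test is itself affected.

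**What to change.** In 12.3 and 12.4, keep Fine-Gray and prespecify alongside it, in both the intention-to-treat and the evaluable populations:

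- (a) a cause-specific Cox model for cognitive failure, with arm and the stratification factors, reporting the hazard ratio and confidence interval;
- (b) the same model for progression or death before cognitive failure;
- (c) the cumulative incidence of that competing event by arm.

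State in advance that a Fine-Gray result, positive or negative, is attributed to an effect of radiation on cognition only when the cause-specific result supports it. Otherwise it is reported as possibly reflecting a difference in tumour control.

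Requiring only that the cause-specific hazard ratio point the same way would be too weak. At a 1.5-fold competing hazard, false benefit in the evaluable-only simulation falls only to 33-35%, and adding a condition to a test cannot restore masked power.

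The cost is SAP wording and two extra models on data already collected; the sample size and primary test are unchanged. The downside is a more qualified conclusion when the measures conflict, resting partly on a hazard that is not itself wholly free of tumour control.

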- 10.2.4 At each two month interval follow up visit out to 2 years all six prespecified cognitive test variables will be assessed. The pattern of cognitive change in memory, executive function, and processing speed will be assessed at each time point. The composite cognitive function

score will be determined by averaging standardized Z-scores from all pre-specified cognitive test variables (5 out of 6 are required to calculate a composite score).

- 10.2.5 MRI imaging including diffusion weighted images (DWI) and reconstructed apparent diffusion coefficient (ADC) maps will be analyzed for differences between pre- and post-treatment scans. They will also be analyzed for differences between the two treatment modalities.
- 10.2.6 Diffusion tensor imaging (DTI) will be analyzed for correlation to the cognitive changes and for differences between the two treatment modalities.
- 10.2.7 Pre-treatment factors of RPA class and MMSE will be assessed for predictive determination of local and distant control and cognitive outcome in each treatment arm.
- 10.2.8 Assessment will be made for correlation between location of primary lesion, total volume of intracranial disease, and cognitive outcome for each of the treatment arms.
- 10.2.9 The relationship between MGMT promoter methylation status and cognitive and local control outcomes will be assessed.
- 10.2.10 Post treatment side effects will be recorded at each follow up visit out to two years. Toxicity will be recorded according the Common Terminology Criteria for Adverse Events v4.0.3 for Nervous System Disorders. Only grade 3 and above toxicity that is directly related to therapy will be required to be documented. Pretreatment symptoms should not be considered as toxicity related to the treatment and are not required to be documented unless the symptoms worsen as a result of therapy.
- 10.2.11 Dosimetric parameters such as dose to the hippocampus will be analyzed for relationship with cognitive and local control outcomes.
- 10.3 Evaluation of correlative markers
 - 10.3.1 Genetic markers: DNA will be extracted within the first five fractions of treatment in the laboratory of the Study Chair. Apo E (i.e., Apo E2, Apo E3, and Apo E4) genes will be analyzed for single nucleotide polymorphisms (SNPs) either by Taqman or direct sequencing.

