We will use descriptive statistics to summarize by treatment arm the quality of life data at each assessment time. We will also use boxplots to summarize the quality of life data by treatment arm at each assessment time. We will model the quality of life data using mixed effects regression methods with repeated measures. The model will include treatment arm, selected dosimetric parameters, baseline cognitive function, location of the primary tumor (left vs. right hemisphere, if bilateral disease is present, location will be determined by the hemisphere with highest burden of disease), and the stratification factors used at randomization as fixed effects and patient as a random effect. We will similarly analyze the cognitive tests. For nearly all the prior mentioned analyses we will also plan to conduct an as-treated analysis.

We will tabulate by treatment arm the adverse events by grade and relationship to treatment.

We will use logistic regression methods to model the logit of the probability of neurocognitive decline as function of ApoE (i.e., Apo E2, Apo E3, Apo E4) genotyping, inflammatory markers (i.e., IL-1, IL-6, TNF- α), and hormone growth factors (i.e., glucocorticoids, gonadal steroids, growth hormone, human chorionic gonadotrpin, insulin-like growth factor-1, neuronal growth factor).

Determination of MCP class will be determined by RPA analysis using results of MGMT, *IDH1*, G-CIMP, and mRNA assays as well as RTOG RPA class. We will use descriptive statistics to report class distributions overall and by treatment arm. Survival by classes will be visualized on Kaplan/Meier plots, compared by the logrank test. The Cox proportional hazards regression will be used to model MCP classification, adjusting for treatment arm and stratification factors.

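### The primary model adjusts for baseline cognition only through two MMSE bands; adding the baseline composite score would recover some efficiency at little cost

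*Combined protocol and SAP*

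**What the plan says.** **Primary model.** Section 12.3 specifies a Fine and Gray model for cognitive failure: "Our model will include treatment arm and the stratification factors used at randomization". Section 7.1 lists those factors as RPA class (III or IV versus V), MMSE (21-26 versus 27-30) and age (under 65 versus 65 or older).

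**Endpoint.** Under 10.1.1, failure is a decline that reaches the reliable change index on any of six variables from HVLT-R, Trail Making and COWA.

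**Baseline data.** Section 8.2 collects these tests before radiotherapy or, where that is not possible, within the first 5 fractions. Section 10.2.4 defines a composite cognitive function score, which "score will be determined by averaging standardized Z-scores from all pre-specified cognitive test variables" and needs five of the six variables.

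**Secondary models.** For quality of life, 12.4 says: "The model will include treatment arm, selected dosimetric parameters, baseline cognitive function, location of the primary tumor". It adds that the cognitive tests will be analysed similarly. No reason is given for using baseline cognition there and not in 12.3.

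**Patients without a baseline.** Under 12.2, evaluable patients must have completed baseline testing. Under 12.3, non-evaluable patients count as treatment failures in the intention-to-treat analysis.

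**The concern.** A change-based endpoint seems to take care of baseline, but it does not. A patient whose baseline score is high partly by chance tends to score lower on retest, and so crosses a reliable change threshold more easily. A patient who starts low tends to drift up, and one near the floor has little room to fall. Baseline score can therefore predict failure even when nobody truly changes.

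Two MMSE bands are a coarse stand-in for scores on six different test variables. With about 30 evaluable patients per arm, the arms can differ by chance on those scores, and the planned model would correct only the part that MMSE captures. At stake are some precision in the primary comparison and a possible argument after the fact about an imbalance that the plan gave no rule for handling.

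**Working it through.** **1. The plan's own figure.** Inputs from 12.2 are one-sided alpha 0.20, 80% power, 4-month failure of 45% versus 30%, exponential times and 1:1 allocation.

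- Hazard ratio = ln(0.70)/ln(0.55) = 0.597, so the log hazard ratio is -0.516.
- Events (Schoenfeld) = 4 × (0.842 + 0.842)² / 0.516² ≈ 42.5, rounded up to 43, as stated.
- Power at 43 events = Φ(0.516 × √43 / 2 − 0.842) = 80.3%.

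No covariate enters this calculation.

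**2. Does baseline predict failure on one test?** The documents give neither retest reliability *r* nor the reliable change cut-off. Assume *r* = 0.6-0.8, a one-sided 5% cut-off and no true change. For a patient with baseline *z* (in SD units), the failure probability is

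Φ{ [z(1 − r) − 1.645√(2(1 − r))] / √(1 − r²) }.

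| r | z = +1 | z = −1 |
|---|---|---|
| 0.6 | Φ(−1.34) = 9.0% | Φ(−2.34) = 1.0% |
| 0.8 | Φ(−1.40) = 8.1% | Φ(−2.07) = 1.9% |

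**3. Does this carry over to any-of-six failure and the composite?** It does, but more weakly. Simulations used reliability 0.6-0.8, inter-test correlation 0.3-0.6, no true change and any-of-six failure set to 45%. The composite's log hazard ratio per SD was 0.09-0.26 with independent test errors, and 0.18-0.62 with errors correlated 0.3-0.6 across tests. The working range is roughly 0.1-0.6.

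**4. Chance imbalance.** With 30 per arm, the SD of the between-arm difference in mean baseline score is √(2/30) = 0.26 SD. If the score correlates ρ with a latent MMSE split at its median, stratification leaves √[(2/30)(1 − 2ρ²/π)]. This is 0.25 at ρ = 0.3 and 0.23 at ρ = 0.6. A 0.25 SD imbalance moves the log hazard ratio by 0.25 × 0.2 = 0.05 or 0.25 × 0.4 = 0.10, against a design effect of 0.52.

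**5. Power.** Cox models were fitted to 6,000 simulated trials per setting: 60 patients, analysis at 43 events, arms balanced within MMSE band, no competing events. The marginal 4-month rates were held at 45% and 30%. The two figures in a cell are for ρ = 0.3 and 0.6.

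| Log HR per SD (HR) | Arm + MMSE | Plus baseline score | Gain, points |
|---|---|---|---|
| 0 (1.00) | 80.5%, 80.5% | 80.2%, 80.2% | −0.3, −0.3 |
| 0.2 (1.22) | 79.3%, 79.5% | 80.1%, 79.9% | 0.8, 0.4 |
| 0.4 (1.49) | 79.3%, 78.8% | 82.2%, 80.9% | 2.9, 2.1 |
| 0.6 (1.82) | 76.8%, 78.5% | 83.2%, 83.7% | 6.4, 5.2 |
| 0.8 (2.23) | 75.3%, 77.8% | 86.2%, 86.1% | 10.9, 8.3 |

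The simulation standard error of each power figure is about √(0.8 × 0.2/6000) = 0.5 points. The gains apply to the 60 evaluable patients. In the intention-to-treat set, failures assigned by rule are unrelated to the score, so the gain there is likely smaller.

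**The case against.** **Baseline cognition is not left out.** MMSE band is balanced by the stratified randomization and is in the model, and each patient's decline is measured from their own baseline. A reader might infer that the model ignores baseline cognition and that the comparison is therefore biased. The documents do not support that. Adjusting for arm and stratification factors is standard, and randomization protects the test. What remains is that the adjustment is coarse.

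**Size and direction are not in the documents.** This stands. The range in step 3 assumes no true change. If patients impaired at baseline truly decline faster, simulation reversed the sign (log hazard ratio −0.2 to −0.7). A fitted covariate copes with either sign, but its strength remains an assumption.

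**Power.** A reader might infer that the trial falls well short of 80%. Larger losses appear if 0.597 is treated as the hazard ratio conditional on baseline. With a log hazard ratio of 0.8 per SD and 45% control failure, that implies 31.9% failure on IMPT, not the 30% in 12.2. Holding the plan's marginal rates gives the table above.

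**The secondary models differ in kind.** They model repeated score levels, where a baseline term is routine. This is fair, and it weakens the contrast with 12.3. It does not answer step 2.

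**Conclusion.** The point holds as a modest, low-cost improvement. The primary model uses a two-band screening score where a finer baseline measure is available, and a decline-based endpoint does not make that measure irrelevant. This is lost efficiency, not a bias or an error, and the stated 43 events and 80% power stand without the change.

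The expected gain is about 0-3 points of power for log hazard ratios up to 0.4 per SD. Gains of 5-11 points need 0.6-0.8 per SD, which no document supports. The steadier reason to act is that MMSE stratification leaves nearly all of the possible chance imbalance in test scores (0.23-0.25 SD against 0.26), so a rule fixed in advance is better than a later dispute.

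These sizes rest on assumed reliability, inter-test and MMSE correlations, and on simulations that, like the plan's own calculation, ignore competing events.

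**What to change.** In 12.3, add the baseline composite Z-score of 10.2.4 as a continuous covariate alongside arm and the stratification factors. Do so both in the primary model and in the evaluable-patient repeat in 12.4.

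For a patient with no composite, fill in one fixed value, such as the mean pooled over both arms, regardless of arm. Do not use a missing indicator. Patients with no baseline are non-evaluable and count as failures by rule, so the indicator would largely encode the outcome and absorb failures that the intention-to-treat rule means to keep in the arm comparison.

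Report the model with arm and stratification factors only as a sensitivity analysis.

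**Cost.** A few sentences in 12.3 and no new data. The model goes from four parameters to five, so events per parameter fall from 43/4 = 10.8 to 43/5 = 8.6. Some baselines will have been taken within the first 5 fractions, so they are not strictly pre-treatment. The number should be reported by arm.
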